8.2.2 Serious adverse events (SAEs)

A serious adverse event is any untoward medical occurrence or effect that:

- Results in death;
- Is life threatening (at the time of the event);
- Requires hospitalization or prolongation of existing inpatients' hospitalization;
- Results in persistent or significant disability or incapacity;
- Is a congenital anomaly or birth defect; or
- Any other important medical event that did not result in any of the outcomes listed above due to medical or surgical intervention but could have been based upon appropriate judgement by the investigator.

An elective hospital admission for other reasons will not be considered as a serious adverse event.

All SAEs that can be related to the surgical procedure that are observed by the local principal investigators or their staff, or reported by the subject between or at the follow up visits, will be recorded in the Case Report Form. The investigator will report all these SAEs to the sponsor within 24 hours after obtaining knowledge of the events by sending the SAE form. SAEs that are related to a previous known or unknown disease, or conditions that cannot be related to the procedure (like accidents or related to other interventions) will not be recorded.

The sponsor will report all reported serious adverse events through the web portal *ToetsingOnline* to the accredited METC that approved the protocol, within 7 days of first knowledge for SAEs that result in death or are life threatening followed by a period of maximum of 8 days to complete the initial preliminary report. All other SAEs will be reported within a period of maximum 15 days after the sponsor has first knowledge of the serious adverse events.

8.3 Follow-up of adverse events

All reported AEs will be followed until they have abated, or until a stable situation has been reached or until the last study visit. Depending on the event, follow up may require additional tests or medical procedures as indicated, and/or referral to the general physician or a medical specialist.

9. STATISTICAL ANALYSIS

The detailed statistical methods and justification are described in Appendix A.

9.1 Primary efficacy analysis

For the primary efficacy analysis, a comparison will be made between the fusion performance of the MagnetOsTM condition and the autograft condition, scored from the one-year (12-15 months) CT-scans according to the method described in Appendix C. Patients that required revision surgery influencing the fusion will be excluded from this analysis. In addition, if one side of a fusion-level is considered not evaluable, this level will be excluded. All evaluable scores will be dichotomized into fusion and no fusion. To allow inclusion of patients with fusion of multiple segments, without increasing the influence of these patients on the outcome, each side in these patients will be statistically considered as one condition. This means that the possible outcomes in these patients are: no fusion (if none of the levels is fused), equal fusion (if an equal number of segments is fused per side) or fusion at one side vs. no-fusion at the other side in case one side contains more fused segments than the other side.

The basis for the primary efficacy analysis will be the test of non-inferiority by performing a McNemar's test. The null hypothesis is that inferiority in fusion rate of the MagnetOsTM Granules compared to the autograft condition is greater than 15% (PAG-PMAG \geq 15%); the alternative hypothesis is that the MagnetOsTM Granules fusion rate will not be lower than the autograft success rate by more than 15% (PAG-PMAG< 15%).

In addition to the McNemar's test, a generalized estimating equations (GEE) model will be used to examine fusion on each side of a vertebra, while accounting for clustering of vertebrae within patients. The outcome will be fusion (yes/no) and the explanatory variable will be treatment. Analysis will result in an odds ratio for MagnetOsTM Granules vs. autograft and a 95% confidence interval.

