Main study parameters/endpoints: The primary efficacy outcome is the rate of successful posterolateral spinal fusion after one year, assessed on CT-scans. Non-inferiority of the MagnetOs™ condition compared to the autograft condition will be assessed using a McNemar's test. The primary safety outcome is the number and nature of (serious) adverse events related to the surgical procedure compared to control populations from literature. Secondary outcomes are the comparison to its predicate (AttraX® Putty), relation between posterolateral fusion and interbody fusion after one-year, posterolateral spinal fusion rate after two years, relevance of iliac crest donor site pain and the incidence of long-term complication and relation with risk factors in the combined population of this study and the AxA study.

Nature and extent of the burden and risks associated with participation: Patient burden and risks are expected to be minimal. The first-year follow-up will be according to the

standard of care at the UMC Utrecht. Additional procedures for this study include the completion of short patient reported outcome measurements at five time points and, depending on the local follow-up protocol, a CT-scan at one-year follow-up and/or X-ray at two years follow-up. In case the one-year CT-scan shows a doubtful fusion or non-union in any of the relevant levels, an additional CT-scan will be made at two years follow-up. Based on pre-clinical investigations, and the results of the AxA study, the risk for inferior performance of MagnetOsTM Granules is expected to be minimal. Even if this appears to be the case, it will have minimal consequences for the patient as the other side of the spine will be fused with autologous bone graft and the spine is rigidly instrumented with screws and bars. All patients may benefit from the study in terms of reduced surgical time, since only half of the required bone graft will be harvested from the iliac crest.

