4.4 Sample size calculation

The primary objective of this study is to demonstrate that treatment with MagnetOsTM Granules is non-inferior to autograft to obtain bony fusion in the spine. The primary outcome is the rate of successful posterolateral bony fusion after one year, assessed at CT-scans. Fusion will be scored binomially and non-inferiority of fusion in the MagnetOs condition will be assessed using a McNemar's test.

Based on literature^{6,28-30,34} and the preliminary results of the AxA study, we estimate a fusion percentage of 50% for unilateral grafting after one year, and a 70% concordance between the left and right side of the fusion trajectory (i.e. both sides fused or non-fused). The non-

inferiority margin is set at an absolute 15% less effectiveness in the MagnetOs condition after one year, which corresponds with 15% less posterolateral sides that are judged as fused. In other words, the rate of fused posterolateral sides in the MagnetOs condition should be more than 35% if the autograft condition shows 50% fusion. We argued that the percentage of the iliac crest graft related complications, ranging from 5% major complications to 40% minor complications, may justify 15% less fusion in a condition that eliminates these complications.

Based on a 1:1 paired assignment of MagnetOsTM Granules to the control condition with autograft, a power of 80%, a one-sided alpha of 0.05 and the non-inferiority margin of 15%, the required sample size for the primary outcome is 84 patients (see Appendix A). We assume that approximately 15% of the included patients will not be evaluable after one year. The intra-patient analyses are not possible when the fusion area has to be revised or when a deep wound infection has occurred and considerable amounts of graft material have to be removed (expected percentage 2-5%). Other failures are lost to follow-up or bad scan quality. Therefore, the total number of patients to be enrolled will be 100.

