9.3 Analysis of secondary outcomes

1. To compare the quantitative primary and secondary results of MagnetOs™ Granules to Attrax® Putty a McNemar's test will be used as well as the mentioned GEE model;
2. As mentioned for the primary analysis, the odds-ratios and 95% confidence intervals for fusion rates of MagnetOs™ Granules and autograft will be calculated by using the GEE model. This model also allows to assess the effect of an additional interbody fusion;
3. For the comparison of the fusion rate after two years, the same method as for the primary efficacy analysis will be used;
4. VAS pain scores will be analyzed using the paired t-test, or Wilcoxon signed rank test in case of not-normally distributed data. To investigate the effect of blinding on perceived donor site pain, pain scores reported by the patients of this study and the AxA study will be compared using the unpaired t-test or Mann-Whitney U test.
5. To investigate risk factors of both study populations regression analysis will be done.

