APPENDIX A. STATISTICAL ANALYSIS

The statistical methods were designed previously for the AxA trial in collaboration with a medical statistician, dr. [name] of the Julius Center, UMC Utrecht, the Netherlands.

Sample size calculation

The numeric results for a non-inferiority (one-sided) test of a difference are shown in the table below. Based on a 1:1 paired assignment of AttraX® Putty to the control condition with autograft, a power of 80%, a one-sided alpha of 0.05, a non-inferiority margin of 15%, an estimated fusion percentage of 50% for unilateral grafting and 70% concordance between both sides of the fusion trajectory, the required sample size for the primary outcome is 84 patients.

Definitions

- Power: probability of rejecting a false null hypothesis;
- N: number of subjects, sample size;
- De: maximum difference between the two proportions that is still called 'equivalent';
- Da: actual difference between Pt and Ps, i.e. Da = Pt-Ps;
- Pt: the response proportion to the treatment (experimental or new) test;
- Ps: the response proportion to the standard (reference or old) test;
- Nuisance Parameter: value that is needed, but is not a direct part of the hypothesis;
- Alpha: probability of rejecting a true null hypothesis;
- Beta: probability of accepting a false null hypothesis.

Power Analysis of Non-Inferiority Tests of Correlated Proportions

Page/Date/Time 19/4/2012 1:37:28 PM

Power	Sample	Equiv.	Actual	Treatment	Standard	Nuisance	Alpha	Beta
	Size (N)	Difference (De)	Difference (Da)	Proportion (Pt)	Proportion (Ps)	Parameter (P01+P10)		
130.10000-0.10000								
0.80005	5889	0.10000	-0.08000	0.42000	0.50000	0.30000	0.05000	0.19995
0.80003	1400	0.10000	-0.06000	0.44000	0.50000	0.30000	0.05000	0.19997
0.80024	591	0.10000	-0.04000	0.46000	0.50000	0.30000	0.05000	0.19976
0.80037	315	0.10000	-0.02000	0.48000	0.50000	0.30000	0.05000	0.19963
0.80135	191	0.10000	0.00000	0.50000	0.50000	0.30000	0.05000	0.19865
0.80000	24761	0.11000	-0.10000	0.40000	0.50000	0.30000	0.05000	0.20000
0.80009	2623	0.11000	-0.08000	0.42000	0.50000	0.30000	0.05000	0.19991
0.80024	899	0.11000	-0.06000	0.44000	0.50000	0.30000	0.05000	0.19976
0.80050	436	0.11000	-0.04000	0.46000	0.50000	0.30000	0.05000	0.19950
0.80053	250	0.11000	-0.02000	0.48000	0.50000	0.30000	0.05000	0.19947
0.80009	158	0.11000	0.00000	0.50000	0.50000	0.30000	0.05000	0.19991
0.80005	6202	0.12000	-0.10000	0.40000	0.50000	0.30000	0.05000	0.19995

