The CT score will be dichotomized into fused and not fused. To allow the inclusion of patients with intended fusion of multiple segments, the sum of fusions on each side of the spine of these patients will be compared. If one side of a fusion-level is considered not evaluable, this will be excluded as well as the contralateral level. In multilevel patients, superiority (in number of fused levels) of one side, will be considered fusion and the other side non-fusion to prevent an unequal influence of patients with multi-level fusions. Although fusion assessment by this method gives more a "relative performance score" than a "fusion rate," analyzing the fusion rate of individual levels will not be adequate. There is strong reason to believe that the fusion rate will vary from patient to patient, so the fusion of individual vertebrae from one patient will not be independent. Since the study is randomized, this dependence should have no effect on a point estimate for the difference in fusion rates for MagnetOsTM Granules vs. autograft, but will certainly affect the standard error of the difference, thereby making standard statistical inference unreliable.

Although we know of no way of generating correct p-values or confidence intervals for differences in fusion rates using clustered data, it is possible to use a multi-level model (in which the clustering of vertebrae within patients is taken into account) to examine the effect of MagnetOsTM Granules and autograft on fusion, and using the vertebrae as the primary level of analysis. Such a model will produce an odds ratio instead of a difference in fusion rates. Since a sample size calculation based on a multi-level analysis requires a number of assumptions that cannot be supported by current data, we decided to perform sample size calculation based on the McNemar's test, and to use the multi-level model as a secondary analysis since it will make better use of the complete data while correctly taking the clustering into account.

Secondary Analysis

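### The primary analysis names McNemar's test, which tests equal rates, against a null of a 15-point deficit; the paired margin test behind N=84 and the rule for declaring non-inferiority are not written down

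*Combined protocol and SAP*

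**What the plan says.** Section 9.1 sets the null as "inferiority in fusion rate of the MagnetOsTM Granules compared to the autograft condition is greater than 15" per cent (in symbols, PAG−PMAG ≥ 15%) and the alternative as a difference below 15%. The same paragraph then says: "The basis for the primary efficacy analysis will be the test of non-inferiority by performing a McNemar's test".

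The same test is named elsewhere:

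- Summary, main study parameters: non-inferiority "compared to the autograft condition will be assessed using a McNemar's test".
- Section 4.4: "non-inferiority of fusion in the MagnetOs condition will be assessed using a McNemar's test".
- Appendix A, primary analysis: "we decided to perform sample size calculation based on the McNemar's test".

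Section 4.4 gives the design values as "a power of 80%, a one-sided alpha of 0.05 and the non-inferiority margin of 15" per cent, with 50% unilateral fusion, 70% concordance and 84 evaluable patients. The Appendix A output is headed "Power Analysis of Non-Inferiority Tests of Correlated Proportions". Its row for a margin of 0.15, true difference 0 and discordance 0.30 reads N=84, power 0.80098.

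Section 9.3, item 3, carries the primary method forward: "For the comparison of the fusion rate after two years, the same method as for the primary efficacy analysis will be used".

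The only interval promised for the efficacy comparison is a 95% interval for an odds ratio from the GEE model. No margin is set on that scale.

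**The concern.** McNemar's test asks whether the two discordant cells have equal probability, that is, whether PAG = PMAG. The 15% does not enter its statistic. The hypothesis in section 9.1 is shifted by 15 points, so the named test and the stated null do not belong together.

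The plan also does not say how a McNemar result becomes a conclusion of non-inferiority. It gives no margin-shifted statistic, no confidence interval for PAG−PMAG, no interval level, and no rule comparing a limit with 15%. The paired table yields a point estimate of the difference, but what is done with it is left open. The method for the main efficacy claim could therefore be chosen after the data are seen. The stated 5% alpha and 80% power also describe a test other than the one named.

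**Working it through.** **Inputs.** From section 4.4 and Appendix A: n=84, margin D=0.15, one-sided alpha 0.05, discordance 0.30, true difference 0. Each patient contributes one pair of sides. Let b be the number of patients fused on the MagnetOs side only, and c the number fused on the autograft side only. The estimate of PAG−PMAG is (c−b)/n.

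**Margin score test.** Z = [D − (c−b)/n] / √(V/n), with V = 2x + D − D². Here x is the maximum likelihood estimate of the MagnetOs-only probability under PAG−PMAG = D. It is the positive root of −2x² + Bx + C = 0. With p=b/n and q=c/n, B = p(1−3D) + q(1−D) − 2(1−p−q)D and C = pD(1−D). Non-inferiority is declared if Z ≥ 1.645.

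**Step 1: reproduce the plan's figure.** Summing exact trinomial probabilities over all (b, c) with discordant cells 0.15 and 0.15:

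| Margin | True PMAG−PAG | N | Printed power | Score test, exact |
|---|---|---|---|---|
| 0.14 | 0 | 96 | 0.80338 | 0.80338 |
| 0.15 | 0 | 84 | 0.80098 | 0.80098 |
| 0.16 | 0 | 75 | 0.80386 | 0.80386 |
| 0.17 | 0 | 66 | 0.80249 | 0.80249 |
| 0.17 | −0.02 | 84 | 0.80146 | 0.80146 |

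(For the last row the cells are 0.14 and 0.16.) These are all the printed rows with N of 100 or less and a true difference of 0 or −0.02. A Wald test with the same margin gives 0.80744 at N=84, so it is not the source. Three larger rows that were checked do not match exact enumeration; for example, at N=115 the print is 0.80255 and the exact value 0.81283. The reason is not given in the documents, and it does not affect the row used.

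**Step 2: type I error of the margin test.** At a true 15-point deficit with discordance 0.30, the cells are (0.30−0.15)/2 = 0.075 and (0.30+0.15)/2 = 0.225. The score test rejects with probability 0.0496.

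**Step 3: the test as named.** The McNemar statistic is (b−c)/√(b+c). With cells 0.15 and 0.15 at n=84, it is significant in favour of MagnetOs at one-sided 0.05 with probability 0.049. That is the size of a superiority test under equality; the 80% power is not a property of this test.

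**Step 4: two adjacent possible results, 25 discordant pairs out of 84.**

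| | 11 vs 14 | 10 vs 15 |
|---|---|---|
| Estimated PAG−PMAG | 3/84 = 0.0357 | 5/84 = 0.0595 |
| x | 0.0921 | 0.0888 |
| V = 2x + 0.15 − 0.0225 | 0.3117 | 0.3050 |
| √(V/84) | 0.0609 | 0.0603 |
| Score Z | 0.1143/0.0609 = 1.88 | 0.0905/0.0603 = 1.50 |
| One-sided p against the margin | 0.030 | 0.067 |
| 90% score upper limit | 13.5% | 15.9% |
| Conclusion | non-inferior | not shown |
| McNemar statistic | −3/5 = −0.6 | −5/5 = −1.0 |
| McNemar p, one-/two-sided | 0.27 / 0.55 | 0.16 / 0.32 |
| Exact McNemar p, one-/two-sided | 0.35 / 0.69 | 0.21 / 0.42 |

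Every version of McNemar's test is non-significant for both results, so it cannot separate them.

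**Step 5: a conditional calculation.** Suppose a non-significant McNemar result were read as non-inferiority. The probability of that at a true 15-point deficit, n=84, is:

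| Discordance | One-sided 0.05 | Two-sided 0.05 |
|---|---|---|
| 0.20 (assumed) | 0.040 | 0.082 |
| 0.30 (plan) | 0.172 | 0.254 |
| 0.45 (assumed) | 0.333 | 0.458 |

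**The case against.** The best defence is that McNemar's test is loose naming for a paired test against the margin. Section 9.1 calls it a test of non-inferiority and states the shifted null beside it. Section 4.4 gives the margin and the one-sided alpha, and illustrates them: with 50% fusion on autograft, MagnetOs should exceed 35%. Section 9 refers the reader to Appendix A, whose output heading concerns non-inferiority tests and whose reference list includes papers on paired non-inferiority. On that view the rule is implied: reject the null at one-sided 0.05.

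Much of this is right. The hypotheses, margin, alpha and sample size are all prespecified, and the authors may well intend a margin test. But no sentence of the analysis text says so. None cites those papers, and Appendix A itself labels the calculation as McNemar's. The 35% illustration does not say whether it applies to an observed rate or to a confidence limit.

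Two further points limit the size of the problem. The false-claim rates in step 5 belong to a rule that the plan does not contain. And if some margin test is used, the choice among forms matters little: at N=84 and 30% discordance, power is 0.8010 for the score form and 0.8074 for the Wald or margin-shifted McNemar form, with type I error 0.0496 and 0.0560. All three forms give the same conclusions for the two results in step 4. Any prespecified paired margin test would close the gap; the score form is preferred because it matches the printed sample size and keeps type I error below 0.05 here.

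**Conclusion.** The concern holds. The test named for the primary endpoint cannot test the null stated in the same paragraph, and the plan gives no statistic, interval or rule that can. The stated 80% power and 5% alpha belong to a margin score test (0.80098 and 0.0496 at N=84), whereas ordinary McNemar favours MagnetOs with probability 0.049 under equality. N=84 is not in dispute.

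That the score test generated N=84 is inferred from agreement to five decimals in five rows; the plan does not name it. The power and type I figures assume the plan's 30% discordance. The 17% and 25% false-claim rates are conditional on reading non-significance as non-inferiority and vary widely with discordance. Because this is the confirmatory analysis of the primary efficacy endpoint, it must be corrected before the data are analysed.

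**What to change.** In the summary, section 4.4, section 9.1 and Appendix A, replace McNemar's test with the score test for a paired difference in proportions, with variance from the restricted maximum likelihood estimate, margin 0.15 and one-sided alpha 0.05. Cite the method in the text.

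State the rule in section 9.1, with its alpha: conclude non-inferiority if the upper limit of the two-sided 90% score interval for PAG−PMAG is below 15%.

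Check section 9.3, item 3, which inherits the primary method, and say which test is meant there. McNemar's test may stay as a superiority test once non-inferiority has been shown. Reporting the GEE result as a risk difference as well is optional.

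The cost is protocol and SAP wording only. The sample size stays at 84 evaluable and 100 enrolled.

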9.2 Primary safety analysis

(Serious) adverse events occurring during the study that may in any way be related to the surgical procedure will be reported in adverse event tables. The frequency and nature of events will be compared to events in control populations from literature.

9.3 Analysis of secondary outcomes

1. To compare the quantitative primary and secondary results of MagnetOs™ Granules to Attrax® Putty a McNemar's test will be used as well as the mentioned GEE model;
2. As mentioned for the primary analysis, the odds-ratios and 95% confidence intervals for fusion rates of MagnetOs™ Granules and autograft will be calculated by using the GEE model. This model also allows to assess the effect of an additional interbody fusion;
3. For the comparison of the fusion rate after two years, the same method as for the primary efficacy analysis will be used;
4. VAS pain scores will be analyzed using the paired t-test, or Wilcoxon signed rank test in case of not-normally distributed data. To investigate the effect of blinding on perceived donor site pain, pain scores reported by the patients of this study and the AxA study will be compared using the unpaired t-test or Mann-Whitney U test.
5. To investigate risk factors of both study populations regression analysis will be done.

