2.2 Secondary objectives

1. To compare the quantitative primary and secondary results of MagnetOsTM Granules to the results of Attrax® Putty from the AxA study (unpaired);
2. To investigate the relation between successful posterolateral fusion and interbody fusion, assessed at the one-year CT-scans used for the primary objective;
3. To compare the posterolateral spinal fusion rate of both MagnetOsTM Granules and autograft at one year with the fusion rates after two years, by using CT-scans;
4. To investigate the effect of blinding on perceived donor site pain, based on outcome measures reported by patients unblinded to the iliac crest donor site in comparison to these outcomes of the blinded patients from the AxA study;
5. To combine the study populations of the current study and the AxA study to investigate a) adjacent segment disease, in relation to length of construct and sagittal balance and b) risk factors for failures.

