2.3 Rationale for secondary objectives

Besides the primary research question on efficacy and safety, this study gives the opportunity to investigate very relevant scientific questions that can only be answered in human patients. Furthermore, combining the study data with the data obtained from the AxA study increases the power to study phenomena that occur less frequently.

1. Comparison of the quantitative results of MagnetOsTM Granules to Attrax® Putty

Since both the study designs are the same and have the same in- and exclusion criteria, it will be possible to compare the groups in a standard unpaired fashion. We did not power this comparison since it is a secondary aim, but the findings will be indicative with a considerable

sample size of 200 individuals (each with autograft at one side of their spine and MagnetOs™ Granules (n=100) or AttraX® Putty (n=100) at the other side).

2. Relation between posterolateral fusion and interbody fusion

Since this study will not exclude interbody fusions, and the effect of such interbody fusions on the posterolateral fusion masses is unknown, it is desired to determine the statistical relation between the posterolateral and interbody fusions.

3. Fusion rate after 2 years

There are indications that the percentage bony fusion continues to increase between 1 and 2 years.²⁶⁻²⁸ Whether this is graft related or a result of immobilization due to instrumentation is unclear. Nevertheless, it is important to determine the long-term fusion potential and behavior of MagnetOs™ Granules and autograft, and to compare these conditions. To limit the number of CT-scans at 2 years follow-up, only those patients that scored a doubtful fusion or non-union in any of the relevant levels at the one-year CT-scan will undergo an additional CT-scan.

4. Relevance of donor site pain

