7.1.2 Secondary study outcomes

1. Comparison of the quantitative primary and secondary results of MagnetOsTM Granules to the results of AttraX® Putty from the AxA study (unpaired);
2. Relation between successful posterolateral fusion and interbody fusion at one-year follow-up (assessed on CT-scans);
3. Posterolateral spinal fusion rate at two years follow-up compared to the fusion rate at one-year follow-up (assessed on CT-scans);
4. Effect of blinding on perceived donor site pain;
5. Incidence of long-term complications and relation with risk factors in the combined population of this study and the AxA study.

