A three-level generalized estimating equations (GEE) model will be used to examine fusion on each side of a vertebra, while accounting for clustering of measurements (fusion on each side of the spine) within spinal levels and within patients. The GEE model will use compound symmetry working correlation matrices for correlation of measurements within vertebrae and vertebrae within patients. In this model, the presence of interbody fusion can also be incorporated as a separate factor. The outcome will be fusion (yes/no) and the explanatory variable will be the treatment condition. Analysis will result in an odds ratio for MagnetOsTM Granules vs. autograft and a 95% confidence interval.

References

1. Lewis, J.A., *Statistical principles for clinical trials (ICH E9) an introductory note on an international guideline*. Statistics in Medicine, 1999. **18**(15), p. 1903-42.
2. Liu, J., et al., *Tests for equivalence or non-inferiority for paired binary data*. Statistics in Medicine, 2002. **21**(2), p. 231-45.
3. Nam, J., *Establishing equivalence of two treatments and sample size requirements in matched-pairs design*. Biometrics, 1997. **53**, p. 1422-30.
4. Nam, J. and Blackwelder, W.C., *Analysis of the ratio of marginal probabilities in a matched-pair setting*. Statistics in Medicine, 2002. **21**(5), p. 689-99.

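### Section 9.3 item 1 assigns McNemar's test, which needs pairs, to MagnetOs versus AttraX Putty, a comparison the protocol itself defines as unpaired

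*Combined protocol and SAP*

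**What the plan says.** Secondary objective 1 in section 2.2 compares MagnetOs with AttraX "Putty from the AxA study (unpaired"), and section 7.1.2 repeats the label for the matching outcome. Section 2.3 gives the reasoning: the two trials share a design and eligibility criteria, so "it will be possible to compare the groups in a standard unpaired fashion". It counts 200 individuals, each with autograft on one side and either MagnetOs (100) or AttraX (100) on the other, and adds: "We did not power this comparison since it is a secondary aim, but the findings will be indicative".

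Section 9.3 item 1 then assigns the methods: "Putty a McNemar's test will be used as well as the mentioned GEE model". Section 9.1 describes that GEE as a model to "examine fusion on each side of a vertebra, while accounting for clustering of vertebrae within patients". Appendix A gives it compound-symmetry working correlations, and of its content says: "explanatory variable will be the treatment condition. Analysis will result in an odds ratio for MagnetOsTM Granules vs. autograft". It also allows an extension: "In this model, the presence of interbody fusion can also be incorporated as a separate factor". Neither section mentions a study term, AttraX as a treatment level, or a MagnetOs versus AttraX contrast.

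**The concern.** McNemar's test uses only discordant pairs, that is, two binary results on the same unit that disagree. Within one trial the pair is the left and right side of one patient. Between MagnetOs and AttraX there is no such unit, because the products were given to different people in different trials.

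An analyst following item 1 literally would have to invent a pairing across trials or fall back on one McNemar test per trial. The first gives a p-value that depends on an arbitrary ordering. The second gives two product-versus-autograft results and no comparison of the products. At stake is whether one of the two methods named for secondary objective 1 can answer it.

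**Working it through.** **1. Is there a pair?** Section 2.3: 200 individuals, autograft on one side of each, MagnetOs in 100 and AttraX in the other 100. Patients with both products: none. Rule for matching patients across trials: none given. Pairs available for MagnetOs versus AttraX: zero.

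**2. The plan's own figure, and where pairing does apply.** The documents state no sample size or power for this comparison. The 84 patients of section 4.4 and Appendix A belong to MagnetOs versus autograft. With 70% concordance (discordance 0.30), margin 0.15, one-sided alpha 0.05 and 80% power, the Wald formula gives N = 0.30 × (1.645 + 0.842)² / 0.15² = 82.4, so 83. The matched-pairs score test, enumerated at N = 84, has power 0.80098, as in the Appendix A table. The figure reproduces. The 70% concordance is between two sides of one patient and does not carry over to patients of different trials.

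**3. McNemar within each trial.** In the current trial it contrasts MagnetOs with autograft. In AxA it contrasts AttraX with autograft. Neither result, nor the pair read side by side, is a test or estimate of MagnetOs versus AttraX.

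**4. What an invented pairing would do (illustration, assumed inputs).** Assume 85 evaluable single-level patients per trial (100 less the 15% of section 4.4, applied to both), with 51 fused in one and 38 in the other (60% and 45%). If k pairs are fused in both members, the discordant counts are b = 51 − k and c = 38 − k. McNemar's chi-square is (b − c)²/(b + c) = 169/(b + c). Over all random pairings k is hypergeometric (85, 51, 38).

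- Central 95% of pairings: b + c from 35 (169/35 = 4.83, p = 0.028) to 53 (169/53 = 3.19, p = 0.074).
- p < 0.05 needs 169/(b + c) > 3.84, so b + c of 43 or fewer. The expected b + c is 43.4, which is why the share below 0.05 is close to even (55%).
- Unpaired chi-square, same data: 170 × (51 × 47 − 34 × 38)² / (85 × 85 × 89 × 81) = 3.985, p = 0.046 for any ordering.

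Sensitivity to the second count, with 51/85 held fixed:

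| Second group fused | Unpaired p | Share of pairings with McNemar p < 0.05 |
|---|---|---|
| 40/85 | 0.091 | 0.7% |
| 39/85 | 0.065 | 8% |
| 38/85 | 0.046 | 55% |
| 37/85 | 0.032 | 95% |
| 36/85 | 0.021 | 99.9% |

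The dependence of p on ordering is general. A change in the significance verdict is likely only when the unpaired p lies near 0.05.

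**5. Can the named GEE supply the contrast?** Code graft (ceramic 1, autograft 0), study (current 1, AxA 0) and their product, with coefficients β1, β2 and β3 and intercept β0. The log-odds of fusion are β0 + β1 + β2 + β3 for MagnetOs and β0 + β1 for AttraX. The direct log odds ratio is therefore β2 + β3. Anchored on each trial's autograft it is (β1 + β3) − β1 = β3. The model can answer the objective, and the two contrasts differ by β2, the between-trial difference on the autograft side.

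**The case against.** The strongest reply is that little is broken. A usable method is already named beside McNemar's test, with outcome, clustering and working correlation given, and AttraX can enter as a further treatment level. The comparison is expressly unpowered and indicative. Section 2.3 gives a basis for comparability, Appendix A already concedes that the multilevel score is a relative measure, and items 4 and 5 of section 9.3 cover cross-trial pain scores and risk factors with unpaired tests and regression. All of this stands, and it limits the weight of the point. It does not rescue the test that item 1 assigns to the comparison.

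A charitable reader might take item 1 to mean one McNemar test per trial. The text does not say so, and step 3 shows that this would not meet the objective.

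Stronger readings should be resisted:

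- A reader might infer that secondary objective 1 has no valid analysis. The GEE is named and open to added factors. Its unwritten coding for pooled data is mostly missing detail.
- A reader might take the 55% as the size of the error. The plan nowhere proposes random pairing, and the table shows that the figure follows from the counts chosen.
- A reader might say the coding must be fixed before AxA is known. Section 1 reports AxA one-year follow-up complete and cites preliminary results, so that is no longer possible. It can still precede the MagnetOs results.
- A reader might hold that the direct contrast is the only right one. The unpaired label permits either. The direct contrast mixes product with trial; the anchored one uses the own-control logic of section 3.

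**Conclusion.** Item 1 of section 9.3 is wrong as written. It names a paired test for a comparison that three other places in the same document call unpaired and that has no pairs. This rests on the text alone and needs no assumption. The numerical illustration rests on assumed counts and shows only that an invented pairing makes the p-value arbitrary.

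The reach is one secondary, unpowered comparison. Nothing here bears on the primary non-inferiority test or its sample size. The correction should be made because it is cheap and because the item, followed literally, would give either an arbitrary result or none for its objective.

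**What to change.** Delete McNemar's test from item 1. Make the GEE the analysis for secondary objective 1, fitted to the pooled level-by-side fusion data of both trials, with graft, study and graft-by-study terms and clustering on patient. Report a MagnetOs versus AttraX odds ratio with 95% confidence interval.

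The sponsor should choose the direct (β2 + β3) or the autograft-anchored (β3) contrast as lead, record the choice before the MagnetOs one-year results are known, and report the other as a sensitivity analysis. Add that the relative side score used for multilevel patients in section 9.1 is not to be compared across trials as a fusion rate, since it depends on the opposite side.

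The cost is SAP wording. The downside is that the direct contrast does not remove between-trial differences, including any in CT grading. Appendix C draws on AxA experience, but the documents do not say that AxA scans were graded by the same rules, so the SAP should state whether they were.
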